7.4 Serious Untoward Medical Events / Serious Adverse Events

An SAE is an AE that lead to serious deterioration in the health of the subject, that resulted in one or more of the below:

- death, or
- an immediately life-threatening illness or injury, or
- a permanent impairment of a body structure or a body function, or
- in-patient or prolonged hospitalization, or
- requires intervention to prevent life-threatening illness, or injury or permanent impairment to a body structure or a body function, or
- led to fetal distress, fetal death or a congenital abnormality or birth defect.

NOTE: Planned hospitalization for a pre-existing condition, or a procedure required by the current CIP, without serious deterioration in health, is not considered an SAE.

A serious adverse device effect (SADE) is an ADE that has resulted in any of the consequences characteristic of a SAE.

An unanticipated serious adverse device effect (USADE) is a SADE, which by its nature, incidence, severity, or outcome has not been identified in the current version of the risk analysis report

NOTE: Anticipated serious adverse device effect (ASADE) is an effect, which by its nature, incidence, severity, or outcome has been identified in the risk analysis report. The classification of an untoward medical event as USADE or ASADE will be done retrospectively. The event will initially be captured as an SAE.

7.5 Definitions of Adverse Event Ratings

7.5.1 Severity

Untoward medical events / AEs will be rated concerning their severity. The rating will be done by the Investigator. The rating used will be the following:

Mild: Transient symptoms, no interference with daily activities of the participant;

Moderate: Clear symptomatology that moderately affects the daily activities of the participant; or

Severe: Symptoms that clearly affects or hinders daily activities of the participant.

7.5.2 Relatedness

The Investigator's assessment of an AE's relationship to the device is part of the documentation process, but it is not a factor in determining what is or is not reported in the study. If there is any doubt as to whether a clinical observation is an AE, the event should be reported. The likely relationship of an AE to the device should be assessed by the Investigator according to the following definitions:

Not Related: Relationship to the device or procedures can be excluded when:

- the event is not a known^a side effect of the product category the device belongs to or of similar devices and procedures;
- the event has no temporal relationship with the use of the investigational device or the procedures;
- the serious event does not follow a known response pattern to the medical device (if the response pattern is previously known) and is biologically implausible;
- the discontinuation of medical device application or the reduction of the level of activation/exposure – when clinically feasible – and reintroduction of its use (or increase of the level of activation/exposure), do not impact on the serious event;
- the event involves a body-site or an organ not expected to be affected by the device or procedure;
- the serious event can be attributed to another cause (e.g. an underlying or concurrent illness/ clinical condition, an effect of another device, drug, treatment or other risk factors);
- the event does not depend on a false result given by the investigational device used for diagnosis^b, when applicable;
- harms to the subject are not clearly due to use error;
- In order to establish the non-relatedness, not all the criteria listed above might be met at the same time, depending on the type of device/procedures and the serious event.

Unlikely: The relationship with the use of the device seems not relevant and/or the event can be reasonably explained by another cause, but additional information may be obtained.

Possible: The relationship with the use of the investigational device is weak but cannot be ruled out completely. Alternative causes are also possible (e.g. an underlying or concurrent illness/ clinical condition or/and an effect of another device, drug or treatment). Cases were relatedness cannot be

^a When the event is not a known side effect of the product category the device belongs to or of similar devices and procedures, generally is considered "not related". Yet, the unexpected effect shall not be excluded from evaluation and reporting.

^b If an investigational device gives an incorrect diagnosis, the patient might, for example, receive an unnecessary treatment and incur all the risks that accompany that treatment, or might be incorrectly diagnosed with a serious disease. In other cases, the patient might not receive an effective treatment (thereby missing out on the benefits that treatment would confer), or might not be diagnosed with the correct disease or condition.

assessed or no information has been obtained should also be classified as possible.

Probable: The relationship with the use of the investigational device seems relevant and/or the event cannot reasonably explained by another cause, but additional information may be obtained.

Causal Relationship: The serious event is associated with the investigational device or with procedures beyond reasonable doubt when:

- the event is a known side effect of the product category the device belongs to or of similar devices and procedures;
- the event has a temporal relationship with investigational device use/application or procedures;
- the event involves a body-site or organ that
 - the investigational device or procedures are applied to;
 - the investigational device or procedures have an effect on;
- the serious event follows a known response pattern to the medical device (if the response pattern is previously known);
- the discontinuation of medical device application (or reduction of the level of activation/exposure) and reintroduction of its use (or increase of the level of activation/exposure), impact on the serious event (when clinically feasible);
- other possible causes (e.g. an underlying or concurrent illness/ clinical condition or/and an effect of another device, drug or treatment) have been adequately ruled out;
- harm to the subject is due to error in use;
- the event depends on a false result given by the investigational device used for diagnosis^a, when applicable;
- In order to establish the relatedness, not all the criteria listed above might be met at the same time, depending on the type of device/procedures and the serious event.

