1.3.2 Clinical Data

The GDL-and-NaG-containing investigational device, *Gedea Pessary* (commercial name *pHyph*), has not been tested in previous clinical trials. Products containing polymerized lactic acid have comparable properties to Gedea Pessary, as lactic acid and GDL have the same ability to inhibit bacterial biofilm formation and lower the pH to a similar extent, see IB. One such product, *Laccure Pessary* (Laccure AB, Helsingborg, Sweden), is buffered to pH 3.5, whereas Gedea Pessary is buffered to pH 3.6. Laccure Pessary has been tested in a clinical trial of 126 patients with confirmed BV, where 93 patients were treated with 1 or 2 doses of Laccure Pessary and 33 patients formed the control group.³⁸ The study showed an 80% cure rate for the single-dose treatment. Most adverse events (AEs) reported were of mild intensity and brief. The most common event was vaginal itching, experienced less than 20% of patients. No serious adverse events (SAEs) occurred and the treatment had no visually detectable negative impact on the vaginal mucosa.

Based on published studies on current treatments for BV, oral, topical, and intravaginal antibiotics are generally well tolerated; reported AEs include nausea, headache, diarrhea, vaginal discharge, and vulvovaginal pruritus. The reported frequencies of AEs after treatment with antibiotics are between 4.6% to 42%, depending on antibiotic used and route of administration.^{16,25,27,39}

Collectively, pre-clinical data indicate that GDL and NaG are safe and may be an effective topical treatment for BV, and a GDL-and-NaG-containing slow-release pessary is to be investigated in this clinical trial.

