7.10.2 Adverse Events

Adverse events will be coded according to MedDRA.

Only treatment-emergent adverse events, i.e. adverse events starting after administration of first dose of study treatment, will be presented as described below. Any adverse events reported to start before administration of first dose of study treatment will be listed separately. In the remainder of this section, the term "adverse event" should be interpreted as "treatment-emergent adverse event".

An overview of all adverse events will be presented, including the number and percentage of patients with at least one, and the total number, of the following:

- Adverse events.
- Serious adverse events.
- Adverse events leading to withdrawal of the investigational product.
- Fatal adverse events.
- Adverse events, broken down by severity (intensity).
- Adverse events, broken down by causality assessment (relationship).

The International Organization for Standardization (ISO) terms ADE, SADE, ASADE, USADE introduced in the CIP constitute adverse events where relationship to investigational device or study procedure is indicated. The classification of an untoward medical event as USADE or ASADE will be done retrospectively. The event will initially be captured as a serious adverse event.

The incidence of adverse events will be presented by system organ class and preferred term. For each system organ class and preferred term, the total number of adverse events as well as the number and percentage of patients with at least one adverse event in that system organ class or preferred term will be presented. The incidence of serious adverse events will be presented in the same way.

Separate tables for the incidence of adverse events broken down by severity and the incidence of adverse events broken down by causality assessment will also be presented by system organ class and preferred term.

There will also be tables on the most frequently reported adverse events, on system organ class level and on preferred term level. The decision on the frequency cut-off for these tables will be taken during the analysis of the adverse events data in consultation with the author of the clinical study report and could be influenced by factors such as the overall number of adverse events, study design, and the nature of the indication. The frequency cut-off should be mentioned in a table note.

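### The relatedness rule treats novelty as a general ground for rating an event 'Not Related', which biases the device-related adverse event counts downwards in a first clinical study

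*Protocol*

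**What the plan says.** Protocol 7.5.2 defines five ratings: Not Related, Unlikely, Possible, Probable and Causal Relationship. The list for 'Not Related' opens with "Relationship to the device or procedures can be excluded when", and its first criterion is that the event is not already a known side effect. Footnote a, attached to that criterion, says that an event which is "not a known side effect of the product category the device belongs to or of similar devices and procedures, generally is considered 'not related". It then adds: "Yet, the unexpected effect shall not be excluded from evaluation and reporting". The list closes with "In order to establish the non-relatedness, not all the criteria listed above might be met at the same time", and no minimum number of criteria is given. Being a known side effect is also the first criterion for 'Causal Relationship'.

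'Possible' is defined as follows: "The relationship with the use of the investigational device is weak but cannot be ruled out completely". Cases that cannot be assessed are added to it. Neither 'Possible' nor 'Probable' requires the effect to be known.

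Protocol 1.3.2 says the pessary "has not been tested in previous clinical trials".

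The rating is used in the results. Protocol 9.2.3.2 presents adverse events by relationship to treatment. SAP 7.10.2 lists "Adverse events, broken down by causality assessment (relationship" among its overview tables and identifies the device-effect terms (ADE, SADE, ASADE, USADE) by whether a relationship is indicated. It does not say which of the five ratings qualify.

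**The concern.** Whether an effect is already known depends on what earlier products and studies have shown. It says nothing about whether the pessary caused the event in front of the investigator. The test has some value for a product with a long record. In a first clinical study that record has to be borrowed from other products, and finding effects not seen before is part of the purpose.

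What is at stake is attribution. A new reaction rated 'Not Related' leaves the related-event breakdown and the ADE and SADE counts. If it is serious and new in nature, it also leaves the USADE count. The default itself can only move an event towards 'Not Related', so its bias favours the device.

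**Working it through.** The plan states no figure on this point, so the main check sets the passages side by side.

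1. **What the default tests.** Footnote a asks only whether the event is known for the product category or similar devices. Timing, body site, response to stopping and other causes appear as separate criteria in the list, and the footnote does not refer to them.

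2. **Whether novelty alone can be enough.** The list says that not every criterion has to be met and sets no minimum. It does not say that one is sufficient. The footnote, however, attaches the 'generally not related' outcome to this single criterion.

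3. **What is left for non-serious events.** In the 'Not Related' list, the criteria on response pattern, response to stopping and another cause are worded for the serious event. For a non-serious event, the main cause-based grounds left are timing and body site, so novelty carries more weight.

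4. **Conflict with 'Possible'.** Take a vulvovaginal reaction of a kind not seen before that starts during dosing. The footnote points to 'Not Related'. The definition of 'Possible' also fits, because a link cannot be ruled out. Neither passage says which prevails, so two sites could rate identical events differently.

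5. **What the footnote's second sentence does.** It keeps the unexpected effect in evaluation and reporting. It does not say how to rate it, and the related-event tables use the rating.

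**Illustration of size.** The number of women, 24, is from Protocol 4.1. The true rate *p* of a new device-caused reaction and the share *q* of such reactions rated 'Not Related' by default are assumptions; the documents give neither. The chance that at least one case is rated related is

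1 − (1 − p(1 − q))^24

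| p | q = 0 | q = 50% | q = 80% | q = 100% |
|---|---|---|---|---|
| 5% | 70.8% | 45.5% | 21.4% | 0% |
| 10% | 92.0% | 70.8% | 38.4% | 0% |
| 20% | 99.5% | 92.0% | 62.5% | 0% |

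For example, with p = 10% and q = 50%, 1 − 0.95^24 = 0.708. The expected number of such women is 24 × 0.10 = 2.4, of whom 2.4 × 0.5 = 1.2 would be rated related. The count in the table of all treatment-emergent events is the same at every value of q.

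**The case against.** The strongest reply is that the footnote is hedged and sits among safeguards. It says 'generally'. 'Possible' and 'Probable' are open to an event nobody has seen before, and 'Possible' is not confined to events that cannot be assessed. Protocol 7.5.2 states that relatedness does not decide what is reported. Protocol 7.7 has every serious event reported. The co-primary endpoint is all treatment-emergent events whatever their cause, and it is descriptive only. The known effects are not an empty list either: Protocol 1.3.2 names vaginal itching with a comparable pessary and discharge and pruritus with antibiotics, and 3.2.1 names discomfort at insertion. The investigator's brochure, which is not available here, may name more.

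All of this stands, and it limits the point to attribution. It does not remove the conflict: the safeguards govern capture and reporting, while the default governs the rating.

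A reader might go further and infer that the USADE category is close to empty by construction, since an effect must be related to count there and an unknown effect is by default unrelated. The documents do not support that. Protocol 7.4 defines a USADE as a serious device effect "which by its nature, incidence, severity, or outcome has not been identified in the current version of the risk analysis report". That is a different reference from the footnote's. A known effect that is more frequent or more severe than the risk analysis report identifies still qualifies, as does a known effect missing from that report, or a new effect rated 'Possible' or 'Probable'. Only USADEs that are new in nature are exposed, and they are still captured as serious adverse events.

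**Conclusion.** The point holds as a bias in the relatedness rating. The footnote and the first 'Not Related' criterion make lack of prior knowledge a general ground for excluding a relationship, which suits a first clinical use poorly and conflicts with 'Possible'. The related-event breakdown, the ADE and SADE counts and the USADEs that are new in nature are biased downwards.

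The size depends on how often investigators follow the default, which the documents do not fix. At an assumed true rate of 10%, defaulting half of the new reactions lowers the chance of any related case among 24 women from 92.0% to 70.8%; defaulting 80% lowers it to 38.4%. A count of zero by rule would need the default to be applied every time, which the word 'generally' does not require.

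A reader might also infer that new reactions vanish from the safety results, or that the trial cannot detect them. They do not vanish: they remain in the all-causality tables, and serious ones are reported whatever the rating.

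**What to change.** In Protocol 7.5.2, replace the first sentence of footnote a with: *Because the device has not been used clinically before, absence from the known side effects is not by itself a reason to rate an event Not Related.* Keep the second sentence.

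Then state that 'Not Related' needs at least one of the existing cause-based criteria: no temporal relationship, a body site not expected to be affected, or attribution to another cause. Apply this to serious and non-serious events alike. Where none is met, the other existing categories apply.

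As an optional clarification, SAP 7.10.2 could state which of the five ratings count as device-related.

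The cost is a short wording amendment; no new data are needed. The device-related event rate may come out slightly higher.

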7.5.3 Outcome

The outcome or the result of the untoward medical event / AE for a participant will be rated by the Investigator as;

Resolved: Fully recovered spontaneously or after medical or surgical intervention, i.e., the status is the same as the pre-study status.

^a If an investigational device gives an incorrect diagnosis, the patient might, for example, receive an unnecessary treatment and incur all the risks that accompany that treatment, or might be incorrectly diagnosed with a serious disease. In other cases, the patient might not receive an effective treatment (thereby missing out on the benefits that treatment would confer), or might not be diagnosed with the correct disease or condition.

Resolved with sequelae:	As a result of the event the participant has remaining significant symptoms or loss of function as, but not limited to, blindness, deafness, or paralysis. All untoward medical events that the participant has not fully recovered from and has significant remaining symptoms or loss of function should be handled as serious untoward medical events / SAEs.
Ongoing:	The status of the participant has not improved and the symptoms are unchanged.
Death	
Unknown:	The status of the participant is unknown. This term is to be used only when no other term applies, e.g., when the participant is lost to follow-up.

7.6 Capturing and Reporting of Untoward Medical Events / Adverse Events

Patients shall be asked about AEs at all visits (both site visits and telephone contacts). Questions for collecting AEs are specified in [Appendix 1, Section 4](#).

Adverse events can also be obtained from:

- Signs and symptoms from patient examinations,
- Laboratory values, or
- Spontaneous reports by subjects or their relatives.

All AEs and ADEs, will be captured in the section for AEs in the eCRF or in case of serious events in the section for SAEs, SADEs, or USADEs.

All events fulfilling the definition of untoward medical event will be captured and reported from the time when the participant signs the ICF and to the last visit in the study or until the participant has left the study. Untoward medical events may need follow-up after the last visit in the study before being rated as recovered or given a final status according to the definitions above.

7.7 Reporting of Serious Untoward Medical Events / Serious Adverse Events

The Investigator will report any SAE to the Sponsor authorized representative **immediately but not later than within 24 hours after awareness** that the event has occurred by completing the SAE eCRF pages.

Further reportable events, according to MEDDEV 2.7.3 rev. 3 have to be reported by the Sponsor/authorized representative to the National Competent Authority (NCA) where the event occurred using an SAE Report Table.

The following events are considered reportable:

- Any SAE
- Any device deficiency (See [Section 7.9](#)) that might have led to a SAE if:
 - suitable action had not been taken or
 - intervention had not been made or
 - if circumstances had been less fortunate
- New findings/updates in relation to already reported events.

The following timelines apply in case of:

- Serious public health threat:
 - Immediately, but not later than 2 calendar days after awareness by Sponsor.
- Death or unanticipated serious deterioration in state of health:
 - Immediately, but not later than 2 calendar days after awareness by Sponsor.
- Others:
 - Immediately, but not later than 7 calendar days after awareness by Sponsor.

7.8 Follow-up of Untoward Medical Events / Adverse Events

Any AE that is ongoing when the patient is withdrawn from the investigation should be followed-up until the AE is resolved or the Investigator decides that the AE is stable and needs no further follow-up. The last day for follow-up will be the study Day 35/42. AEs ongoing at study Day 35/42 shall be assessed as chronic or stable.

7.9 Device Deficiencies

A device deficiency will in this study be defined as an inadequacy of a medical device with respect to its identity, quality, durability, reliability, safety^a, or performance.

All device deficiencies related to the identity, quality, durability, reliability, safety or performance of an investigational medical device shall be documented in the eCRF. Device deficiencies include malfunctions, use errors, and inadequate labeling.

7.10 Tolerability

Based on AEs

7.11 Pregnancy

Subjects must be instructed to immediately inform the Investigator if any pregnancy should occur from the time of signing the informed consent form and 6 weeks onwards. Any confirmed study-subject pregnancy shall be reported by the Investigator on a Pregnancy Report Form immediately but not later than 24 hours of awareness and submitted to the Sponsor-authorized representative. Subjects becoming pregnant will be withdrawn from the study and followed until delivery, additional information on the infant will be collected until the infant is 1 month old. Adverse events in connection with the pregnancy, in the fetus, and in the infant up to 1 month of age will be reported. Any abortions (including elective abortions) together with abortion rationale should be reported and handled as SAEs; as well as any complications relating to the pregnancy, fetus, and infant fulfilling any criteria for seriousness. Procedures and timelines for AE/SAE reporting applies to reporting of AEs/SAEs in the pregnant subject, the fetus, and the infant.

^a Inadequacy of device safety refers to properties of the device that could have or have led to an AE.

Protocol Version 2.1, 27 Jun 2019

LINK Medical Research | Protocol template

Version 2.0 | Effective date 17Apr2018

